## **Aims**

The specific aims of this Phase 1 therapy development project are to:

*Aim 1:* Compare number of completed daily self-monitoring surveys in CM and C groups. One hypothesis was tested:

*Hypothesis 1:* CM group participants will complete more daily self-monitoring surveys compared to control group participants.

*Aim 2:* Compare longest sustained period of daily survey completion in CM and C groups. One hypothesis was tested:

*Hypothesis 1:* CM group participants will have a longer sustained period of daily survey completion compared to control group participants.

*Aim 3:* Examine agreement between daily survey and follow-up visit reports of alcohol and Rx opioid use in CM and C groups.

*Aim 4:* Examine feasibility and acceptability of CM app implementation targeting self-monitoring of pain severity, related factors, and use of Rx opioids and alcohol.

*Aim 5:* Estimate effect-size to be used to perform power analyses and sample size calculations as part of the design of a larger RCT.

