## **Methods**

### **Participants**

Participants will be individuals seeking to participate in research studies through ResearchMatch.org. Individuals will be eligible to participate in the study if they meet the following criteria: 1) at least 18 years of age; 2) own a study-compatible smartphone (iPhone or Android device); 3) report non-cancer related chronic pain of at least 3 months' duration; 4) able to provide informed consent for study participation; 5) report having chronic pain as part of their ResearchMatch.org profile; and 6) prescribed  $\geq 1$  opioid medication(s) for pain management in their lifetime. Individuals will be excluded from study participation if they meet any of the following criteria: 1) currently pregnant; 2) presenting with language barriers, cognitive impairment, or serious medical or psychiatric illness that in the opinion of the Investigator would preclude them from providing informed consent or participating in the study; and 3) visual impairment or motor impairment that would interfere with use of a smartphone.

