***Follow-Up Survey Only***

**TLFB (Sobell & Sobell, 1992).** The TLFB is a widely-used, semi-structured interview that uses a calendar to retrospectively collect daily information about substance use. It has been shown to have good reliability and validity and is widely considered the “gold standard” of quantity and frequency substance use assessment. To accommodate the remote study procedures, the TLFB was adapted from interviewer to computer administered (via REDCap), which has been found to be reliable and valid (e.g., Martin-Willett et al., 2020). The TLFB was used to obtain detailed past 28-days frequency of opioid pain medication and alcohol use information.

**Acceptability.** Participants were asked to answer questions about satisfaction, acceptability, and feasibility on a 0-10 scale based on those used in a previous RCT investigating an app developed for chronic pain patients (Jamison et al., 2017).

**Validity and Accuracy of Responses.** All participants were asked how honest they were in completing the daily survey (response options: I was very honest, I was honest most of the time, I was honest some of the time, I was honest once in a while, I was not honest at all). CM participants were additionally asked how much the rewards made a difference in how accurately

they reported information in the daily survey (response options: Not at all, very little, little, somewhat, much, to a great extent, completely).

**Self-Report of Impact of Behavioral Incentives to Adherence.** CM participants were asked how much the rewards made a difference in whether they completed the daily survey (response options: Not at all, very little, little, somewhat, much, to a great extent, completely).

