**Table 3**

*Overview of Study Measures*

Measure	Baseline Survey	28-Day Monitoring Period	Follow-Up Survey
Demographic information, medical/mental health history	X		
BPI, PCS, PSEQ, HADS, PSQI	X		X
Daily self-monitoring survey (via app), daily self-monitoring survey completion time		X	
TLFB, acceptability survey, validity of responses			X

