### ***Sample Size Justification***

As this is a Stage I pilot study and no preliminary data are available, a power analysis is not provided. Sample size was determined by anticipating a medium effect size (.05), 80% power, alpha level=.05 (Cohen, 1988). For two-sided *t*-tests, 32 participants/group are needed. This would allow us to detect an effect size of  $d=.711$ , which falls between medium,  $d=.05$  and large,  $d=.8$  effect sizes. Recruitment of 80 subjects with 80% retention was expected to achieve this effect size.

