### ***Outcome Measures***

As shown in Table 4, the primary outcome measures are the number of completed daily self-monitoring surveys and the longest period of sustained adherence to survey completion. It is hypothesized that those in the CM group will complete more daily self-monitoring surveys and have a longer sustained period of daily survey completion compared to controls. The number of completed daily surveys and duration of continuous daily survey completion will be compared between CM and Co groups using independent *t*-tests.

Secondarily, descriptive statistics will be used to summarize CM participants' self-report of the impact of behavioral incentives on adherence. Mean time to complete the daily surveys between CM and Co groups will be compared using an independent *t*-test. Pain experience and

related variables from baseline will be compared to follow up responses for the total sample using paired *t*-tests. The daily survey item responses will be summarized for the overall sample using descriptive statistics. Associations between daily survey and follow-up TFLB for alcohol and prescription opioid use data for the overall sample and each study group will be examined using Spearman's correlations. Descriptive statistics will be used to summarize self-report validity and accuracy of responses. Feasibility and acceptability of CM app implementation will be examined by comparing follow-up acceptability survey ratings for each group using independent *t*-tests.

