**Table 4**

*Outcome Measures Overview*

Name	Time Frame	Brief Description
Number of daily surveys completed	28-day daily survey period	This primary outcome is consistent with previous CM studies.
Longest period of sustained adherence to daily survey completion	28-day daily survey period	Largest number of consecutive days wherein daily surveys were completed. This primary outcome is consistent with previous CM studies.
Mean frequency of alcohol and prescription opioid use (days of use)	28-day daily survey period to follow up	Spearman's correlations between daily survey and TLFB data for alcohol and prescription opioid frequency (days of use) were conducted for the entire sample, the CM group, and the Co group.
Mean time to complete the daily surveys	28-day daily survey period	Daily survey completion time (the amount of time from daily survey start to finish).

Name	Time Frame	Brief Description
Mean CM app feasibility and acceptability survey ratings	Follow up	CM app satisfaction, acceptability, and feasibility survey ratings (on a 0-10 scale; administered at follow-up) based on those used in a previous RCT investigating an app developed for chronic pain patients (Jamison et al., 2017).
Self-report validity and accuracy of responses	Follow up	Ratings of how honest participants were in completing the daily survey and how much the rewards made a difference in how accurately CM participants reported information in the daily survey.

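### Aim 3 is agreement between the daily survey and the Timeline Followback, but the only planned comparison is a rank correlation, which cannot show a systematic gap

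*Combined protocol and SAP*

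**What the plan says.** The Aims section states Aim 3 as: "Examine agreement between daily survey and follow-up visit reports of alcohol and Rx opioid use in CM and C groups". No hypothesis is attached. Under Outcome Measures in the Data Analysis Plan, "Associations between daily survey and follow-up TFLB for alcohol and prescription opioid use data for the overall sample and each study group" are to be examined with Spearman's correlations. Table 4 repeats this as Spearman's "correlations between daily survey and TLFB data for alcohol and prescription opioid frequency (days of use", and says that the correlations "were conducted for the entire sample, the CM group, and the Co group". Table 4 names the outcome as a mean frequency in days of use, but defines no difference between the sources.

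No other planned analysis pairs them. The paired t-tests compare baseline with follow-up pain and related variables. The daily items are summarised on their own, and the honesty and accuracy questions are self-ratings.

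Table 3 places "TLFB, acceptability survey, validity of responses" in the follow-up survey only. The TLFB is described as an instrument that "uses a calendar to retrospectively collect daily information about substance use", here over the past 28 days. The app survey in Appendix A asks about the previous day. It has a tick box for opioids (item 9) and three free-response drink counts for alcohol (items 11-13).

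**The concern.** Agreement asks whether two sources give the same answer for the same person. Spearman's rho asks only whether they rank people in the same order. If the app systematically misses use days that the TLFB holds, the order can survive while the level is wrong. A low rho would reveal poor agreement, but a high one would not show good agreement. Under-recording in the app is the main thing an agreement aim should detect.

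Two features add to this. For opioids, eligibility needs only one or more "opioid medication(s) for pain management in their lifetime", so some participants may have no use in the 28 days, and pairs that are zero in both sources raise rho. The plan also does not define the daily-survey value: it could be a raw count of use days, a share of completed surveys or a count on matched days. Nor does it say how missed surveys enter, in a trial whose premise is poor adherence.

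**Working it through.** The documents give no figure for Aim 3. Their one design figure, 32 per group at d = 0.711, reproduces (32.04 by the noncentral t) but belongs to the primary t-tests. Use patterns, completion rates and the unrecorded share below are assumptions.

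1. **Exact halving.** Let 15 people have TLFB days 0, 2, ..., 28 (mean 14) and app days equal to half of these (mean 7). The ranks are identical, so rho = 1 - 6 x 0 / [15 x (225 - 1)] = 1.00. The mean paired difference is 14 - 7 = 7 days.

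2. **Analysis set.** The sample-size section says: "Recruitment of 80 subjects with 80% retention was expected to achieve this effect size". Applying 80% to the stated arms: 0.8 x 46 = 36.8, about 37 CM; 0.8 x 35 = 28 control; 65 in all.

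3. **Size of the gap, half of use days unrecorded.** Each person's daily use probability is drawn as follows.
   - Intermittent: Beta(1.5, 2), mean 1.5/3.5 = 0.429. Gap 0.5 x 0.429 = 21 points.
   - Alcohol: the same with 30% never-users, mean 0.7 x 0.429 = 0.300. Gap 15 points.
   - Opioids: 50% never, 25% daily, 25% intermittent, mean 0.25 + 0.25 x 0.429 = 0.357. Gap 18 points.

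4. **Rho in the same case.** Raw counts, pooled arms, 85% completion in CM and 55% in control. The ranges run from a wide spread of adherence between people to equal adherence; repeat runs differ by about 0.01.

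| Use pattern | Rho, half unrecorded | Gap (points of days) |
|---|---|---|
| Intermittent | 0.72-0.81 | 21 |
| Alcohol | 0.87-0.92 | 15 |
| Opioids | 0.94-0.96 | 18 |

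   Opioids under perfect reporting give 0.96-0.98 with a matched-day gap of 0. At 90% completion in both arms, the half-unrecorded rho is 0.85-0.97 across the three patterns.

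5. **Never-users.** Opioids, 90% completion, half unrecorded, the remainder split equally between daily and intermittent users. With 30%, 50% and 70% never-users, rho is 0.94, 0.97 and 0.98-0.99. Among users alone it is about 0.83, and their app record is 0.5 x (0.5 x 1 + 0.5 x 0.429) = 0.357, or 36 points, too low in all three cases.

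6. **Why a raw difference in means is not enough.** Intermittent use averages 28 x 0.429 = 12.0 days. With fully honest reporting, missed surveys alone leave the app short by 12.0 x 0.15 = 1.8 days in CM and 12.0 x 0.45 = 5.4 in control. In a separate run with uniform use, honest reporting at 50% completion gave a raw gap of 7.0 days (rho 0.92), and full completion with half of use days denied gave 7.1 days (rho 0.91). On completed-survey days only, the first gap is 0.0.

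7. **Windows.** Surveys 1-28 refer to days 0-27. A TLFB completed on day 29 covers days 1-28 (27 days shared); on day 32, days 4-31 (24 shared); on day 35, days 7-34 (21 shared). The follow-up procedures allow for late completion, with a reminder after two days and a call after three.

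**The case against.** The strongest reply is that Table 4 names the outcome as a mean frequency in days of use. If means were shown by source, a halved app mean would be visible beside the TLFB mean. That is fair, and it rules out saying that the plan must hide under-recording. But no mean by source, paired difference or interval is stated, and step 6 shows that raw means cannot separate missed surveys from unrecorded use.

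A reader might also infer that rho stays high whatever happens. The documents and the arithmetic do not support that. At 85%/55% completion it falls to 0.72-0.81 for intermittent use, and in a separate run with near all-or-none completion averaging 50%, and every surveyed use day reported, it was 0.51-0.76. The case is strong for opioids, fair for alcohol and weaker for intermittent use. A rho lowered by adherence is still not a measure of agreement.

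A third reading is that the arm-specific coefficients bias a comparison of CM with control. No between-arm test is planned, so this matters only if someone compares the two coefficients informally and the daily value is a raw count.

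Finally, the aim is secondary, and the plan's stated major goal is effect sizes for the primary outcomes. That limits the weight of the point but does not remove it.

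**Conclusion.** The point holds: the planned statistic does not answer the stated aim. Exact halving is a mathematical fact and needs no assumption. The illustrative sizes (15-21 points of days too low with pooled rho of 0.72-0.96, and opioid rho of 0.94-0.96 against 0.96-0.98 under perfect reporting) rest on assumed use patterns, completion rates, 80% retention and half of use days unrecorded. None of those rates except retention is in the documents.

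It should be changed, but it is not critical: the primary outcomes and their tests are untouched. A matched-day difference would also not prove denial of use, because both sources are self-report. It covers follow-up completers only.

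**What to change.** In Outcome Measures and Table 4, make the main Aim 3 analysis the participant-level paired difference in proportion of days with use (daily survey minus TLFB), with its mean and bootstrap 95% CI, overall and by arm.

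- Use only completed surveys whose reference day (survey date minus 1) lies inside that participant's TLFB window.
- Do not count missed surveys as no use. Exclude participants with no matched day and report how many there are.
- Define a use day: opioid box ticked in item 9; for alcohol, any of items 11-13 above 0. Say how blank entries are treated.
- Repeat the difference among participants with any use in either source.
- Keep Spearman as descriptive.
- If the TLFB stores only totals, compare the proportion of surveyed days with use with TLFB days/28. State that the windows may differ and that missed surveys are assumed unrelated to use. The fallback depends heavily on this: at 70% base completion, if completion on use days is 0.8 or 0.5 times that on other days, honest reporting still shows a gap of 1-4 or 3-13 points.
- State that both sources are self-report. Label the analysis post hoc if the correlations have already been run; Table 4 is in the past tense.

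The cost is plan wording and modest programming, plus fewer usable days. With full overlap, 37 x 28 x 0.85 = 881 CM and 28 x 28 x 0.55 = 431 control person-days are matched. With 24 shared days these are 37 x 24 x 0.85 = 755 and 28 x 24 x 0.55 = 370. By-arm intervals are wide: at full overlap, half-widths are about 5-7 points in CM and 6-9 in control.

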## Appendix A

### **Daily Self-Monitoring Survey (via DynamiCare Rewards app)**

#### **How were you yesterday?**

1. What was your average pain? (rated on a 0-10 scale; 0=no pain, 10=worst pain)
2. How much did your pain interfere with your daily activities? (rated on a 0-10 scale; 0=did not interfere, 10=completely interfered)
3. Overall, how much have things changed? (rated on a 0-10 scale; -5=worse; 0=the same; 5=better)
4. How would you rate your sleep quality? (Very good (0) Fairly good (1) Fairly bad (2) Very bad (3))
5. How sad were you yesterday? (rated on a 0-10 scale; 0=not at all and 10=very much)
6. How anxious were you yesterday? (rated on a 0-10 scale; 0=not at all and 10=very much)
7. How irritable were you yesterday? (rated on a 0-10 scale; 0=not at all and 10=very much)
8. Did you take any prescription medications yesterday? (Yes or No)
9. [If yes to the above] Which prescription medications did you take? (check all that apply)
  - Prescription opioid pain reliever (for example: Percocet, Vicodin)
  - Prescription medication for anxiety or sleep (for example: Xanax, Ativan, or Klonopin)
  - Other prescription medication (free response)
10. [For those checked above] How did you take the [type of medication]?
  - Took as prescribed
  - Took less than prescribed
  - Took more than prescribed
  - It was not prescribed for me
11. How many 12-ounce beers containing alcohol did you have? (free response)
12. How many 5-ounce glasses of wine did you have? (free response)
13. How many shots of liquor did you have (straight or in a mixed drink)? (free response)
14. Did you use marijuana? (Yes or No)
15. Did you use cannabidiol (CBD)? (Yes or No)

## Appendix B

### Computer-Administered Survey

#### Demographic Information [Baseline Visit Only]

1. Of what race do you consider yourself?
  - a. White or Caucasian
  - b. American Indian or Alaskan Native
  - c. Asian
  - d. Black or African American
  - e. Native Hawaiian or other Pacific Islander
  - f. Other
2. What is your ethnicity?
  - a. Hispanic
  - b. Not Hispanic
3. What is your gender? (Female; Male; Other)
4. What is your age? Click in the box, type your age, and click submit. (free response)
5. What is your current marital status?
  - a. Single
  - b. In a relationship
  - c. Married
  - d. Divorced/separated
  - e. Widowed
6. What is your current employment status?
  - a. Full time, 40 hours per week
  - b. Part time
  - c. Not working due to medical or mental health disability
  - d. Retired
  - e. Unemployed
  - f. Student
  - g. Homemaker or stay-at-home mom
7. What is the highest grade you completed in school?
  - a. Grades 1 through 8
  - b. Grades 9 through 11
  - c. Grade 12 or GED
  - d. Some college
  - e. Associate's degree
  - f. Bachelor's degree
  - g. Technical training (ex: cosmetology, computer, trade school)

- h. Graduate degree (Master's or Doctorate)

12. Who do you currently live with?

- a. With my children and significant other/spouse
- b. With my significant other/spouse only
- c. With my children only
- d. With other family
- e. With friends
- f. Alone
- g. I move around a lot or am homeless
- h. Group home or assisted living facility

**Medical and Mental Health History [Baseline Visit Only]**

1. How many days have you experienced medical problems in the past 30 days? (response 0-30)
2. Check all of the following medical conditions that a doctor, nurse, or other health professional has told you that you have.
  - a. Heart disease (e.g., angina, heart attack, or congestive heart failure)
  - b. High blood pressure
  - c. High cholesterol
  - d. Migraines
  - e. Diabetes
3. As before, check all of the following medical conditions that a doctor, nurse, or other health professional has told you that you have.
  - a. Hepatitis
  - b. Liver disease
  - c. Pancreatitis
  - d. Asthma
  - e. Chronic obstructive pulmonary disease (COPD) (e.g., emphysema or bronchitis)
  - f. Arthritis
  - g. Other (free response)
4. Check all of the following mental health conditions that a doctor, psychologist, or other health professional has told you that you have.
  - a. Depression
  - b. Anxiety
  - c. Bipolar Disorder
  - d. Attention-Deficit/Hyperactivity Disorder
  - e. Substance Use Disorder
  - f. Other (free response)
5. Are you currently prescribed any opioid medications (such as OxyContin, Vicodin, Tylenol 3, Percocet, or morphine)? (yes or no)

6. Are you currently prescribed any other types of pain medications (such as *Gabapentin* or *Pregabalin*)? (yes or no)
7. Are you currently prescribed any benzodiazepine medications (such as Xanax, Ativan, Valium, or Klonopin)? (yes or no)

## The Brief Pain Inventory (BPI) [Baseline & Follow-Up Visits]

1. Throughout our lives, most of us have had pain from time to time (such as minor headaches, sprains, and toothaches). Have you had pain other than these everyday kinds of pain today?

Yes  No

3. Please rate your pain by marking the box beside the number that best describes your pain at its **worst** in the last 24 hours.

□ 0    □ 1    □ 2    □ 3    □ 4    □ 5    □ 6    □ 7    □ 8    □ 9    □ 10  
No Pain  
Pain As Bad As You Can Imagine

4. Please rate your pain by marking the box beside the number that best describes your pain at its **least** in the last 24 hours.

5. Please rate your pain by marking the box beside the number that best describes your pain on the average.

6. Please rate your pain by marking the box beside the number that tells how much pain you have right now.

0    1    2    3    4    5    6    7    8    9    10

No  
Pain  
As Bad As  
You Can Imagine

**7. What treatments or medications are you receiving for your pain?**

8. In the last 24 hours, how much relief have pain treatments or medications provided? Please mark the box below the percentage that most shows how much relief you have received.

9. Mark the box beside the number that describes how, during the past 24 hours, pain has interfered with your:

### A. General Activity

 0	 1	 2	 3	 4	 5	 6	 7	 8	 9	 10
Does Not Interfere										Completely Interferes

## B. Mood

 0	 1	 2	 3	 4	 5	 6	 7	 8	 9	 10
Does Not Interfere										Completely Interferes

### C. Walking ability

0    1    2    3    4    5    6    7    8    9    10

Does Not Interfere      Completely Interferes

#### D. Normal Work (includes both work outside the home and housework)

0    1    2    3    4    5    6    7    8    9    10

Does Not Interfere   Completely Interferes

## **E. Relations with other people**

 0	 1	 2	 3	 4	 5	 6	 7	 8	 9	 10
Does Not Interfere										Completely Interferes

## F. Sleep

 0	 1	 2	 3	 4	 5	 6	 7	 8	 9	 10
Does Not Interfere									Completely Interferes	

## G. Enjoyment of life

 0	 1	 2	 3	 4	 5	 6	 7	 8	 9	 10
Does Not Interfere										Completely Interferes

## **Pain Self-Efficacy Questionnaire (PSEQ) [Baseline & Follow-Up Visits]**

Please rate how **confident** you are that you can do the following things at present, despite the pain. To indicate your answer circle one of the numbers on the scale under each item, where 0= not at all confident and 6= completely confident.

Remember, this questionnaire is **not** asking whether or not you have been doing these things, but rather **how confident you are that you can do them at present, despite the pain**.

1. I can enjoy things, despite the pain.
2. I can do most of the household chores (e.g. tidying-up, washing dishes, etc.), despite the pain.
3. I can socialise with my friends or family members as often as I used to do, despite the pain.
4. I can cope with my pain in most situations.
5. I can do some form of work, despite the pain. (“work” includes housework, paid and unpaid work).
6. I can still do many of the things I enjoy doing, such as hobbies or leisure activity, despite pain.
7. I can cope with pain without medication.
8. I can still accomplish most of my goals in life, despite the pain.
9. I can live a normal lifestyle, despite the pain.
10. I can gradually become more active, despite the pain.

